#### G2. Data Analysis

Provide a description of your plan for data analysis. State the types of comparisons you plan (e.g. comparison of means, comparison of proportions, regressions, analysis of variance). Which is the PRIMARY comparison/analysis? How will the analyses proposed relate to the primary purposes of your study?

Data analysis will involve Multilevel Modeling (MLM) because of the *nesting* nature of the variables. More specifically, because the measures are repeated, the measures are considered the first level of the hierarchy, the individual children are considered the second level, and the treatment groups are considered the third level. A major advantage of MLM is its ability to handle missing data. While more traditional analyses use listwise deletion if a single time point is missing, MLM uses parameter estimates to maximize the use of existing data. Furthermore, the present study will implement a regression discontinuity analysis, which is an application of mixed models within MLM. This will allow us to examine the impact of treatment, without the use of random assignment, as this method allows for the use of groups that are similar at baseline, but then are designated by a predetermined selection cut point.

After assessing responder status and determining which participants receive Step Two treatment and which participants move to the maintenance phase, binary logistic regression will be utilized in an attempt to determine if there are factors significantly predicting group membership. Possible predictors include variables such as age, anxiety severity, internalizing/externalizing problems, and parent characteristics.

Cost-effectiveness analysis examines the relative value of SC-CBT (relative to CBT). CEA is performed from a societal perspective, meaning the costs to the healthcare system and the patient/parents are included. Treatment costs include

direct (e.g., cost of therapy session), indirect (e.g., travel costs, missed work), and opportunity costs (e.g., value of lost time; see above for cost measures). CEA often incorrectly omits the opportunity cost of patient/parent time spent on therapy, phone support, and at-home parent-child meetings. Non-study, mental-health service costs include inpatient, outpatient, and school-based services and will be priced using the Texas Medicaid fee schedules. Research-specific costs (e.g., screening, research consent) for patients and staff are excluded. Incremental cost-effectiveness ratios (ICER) are computed as incremental costs divided by incremental changes in morbidity/outcomes (symptom reduction and change in impairment/functioning). If outcomes differ significantly, a non-parametric bootstrap with replacement method is used to generate a joint distribution of differential costs and outcomes. If outcomes do not differ, cost-effectiveness is determined by examining treatment costs. Mean and median ICER ratios are reported, as well as 95% confidence intervals. Cost-effectiveness acceptability curves examine the probability of falling below a variety of cost-effectiveness thresholds. In addition to the ICER approach, the net-benefit approach will be used to determine if findings are sensitive to method.

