#### TREATMENT

All participants will receive parent-led, stepped-care cognitive-behavioral therapy (SC-CBT). CBT focuses on how a child's thoughts, beliefs, and attitudes affect feelings and behavior and teach children coping skills for dealing with different problems. The type of CBT that will be used is a specialized program for children and adolescents with ASD and comorbid anxiety. This type of treatment will be delivered using a stepped-care model, which provides therapy in "steps" that vary by intensity. Treatment is "stepped-up" until the child begins to show improvement in anxiety symptoms, beginning first with the lowest intensity (e.g., fewer in-person appointments, parent-led exposures) to more intensive (e.g., weekly in-person sessions, therapist-led exposures), as needed. SC-CBT consists of two main steps (detailed below). Each participant will be treated by a licensed psychologist/therapist or trainee under the supervision of a licensed psychologist. At the end of study participation, a standardized summary of assessment and treatment will be provided to research participants. Assessment summaries will contain information about inclusion criteria (e.g. SRS score, CSR score, PARS score, whether they met IQ cut off, etc.). It will be specified that this summary details research findings, and that our assessment is not equivalent or a substitution of a clinical evaluation. Treatment summaries will contain information about how many therapy sessions participants attended. Summaries will be reviewed and signed by PI before sharing them with research participants. Summaries will be shared through secure email, postal mail, or in person.

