**STEP ONE.** All participants will start with Step One, which includes 4 parent-led, therapist-assisted sessions over a 12-week period. Parents will receive a parent-child workbook to use in session with the therapist, and at home. During each of these 4 sessions, the therapist will review with parents the necessary skills for conducting exposures and will provide guidance in the delivery of exposures. Exposures, a hallmark of CBT for anxiety are used to gradually and repeatedly confront feared stimuli. For example, exposure therapy for a child fearful of dogs may begin with looking at pictures of dogs and standing across the park from a dog on a leash, to eventually petting a dog. Outside of session, parents will lead therapy using the provided workbook, which consists of a step-by-step approach for parents written on a 6th-grade level. Brief phone contacts between parent and staff will also be provided for support, coaching, and motivation. After completing Step One, a brief assessment will occur (i.e., the mid-treatment). If the child meets treatment response status, then the parent and child end treatment and proceed to the Maintenance phase, where parents and children will be encouraged to continue using the workbook and tools that they learned in Step One. If the child does not meet treatment response (i.e., does not improve), then s/he will 'step up' to Step Two.

**STEP TWO.** For those children who do not respond to Step One, they will be 'stepped up' to Step Two, which consists of 10 therapist-led, parent-supported sessions, each lasting 60-120 minutes over the course of 12 weeks. During Step Two, therapists will lead exposure tasks and teach children response strategies. These strategies will focus on providing children with anxiety-coping skills. In addition, parents will be taught (in weekly sessions) to support children in learning and maintaining anxiety-coping skills, especially when outside of sessions. These skills are encouraged to be practiced at school, in the community, and in peer-group settings. After completing Step Two, participants will end treatment and the post-assessment will occur. For those participants in the maintenance phase (i.e., treatment responders at Step One), the post-assessment will occur approximately 12 weeks after the completion of the mid-treatment (for consistency with procedures in Step Two). All participants will then be re-assessed 3-months, after completion of the post-treatment.

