### Section G: Sample Size/Data Analysis

#### G1. Sample Size

How many subjects (or specimens, or charts) will be used in this study?

Local: 200      Worldwide: 200

Please indicate why you chose the sample size proposed:

We will enroll a total of 200 participants, which achieves sufficient power for the primary and secondary aims. Although we expect slight attrition, the below-mentioned analyses allow for attrition without the loss of data. While MLM does not provide for specific power analyses, the suggested power rules range from 20 participants per group, per level. As such, to be conservative with our power estimates, we aim to enroll 200 participants to ensure we are sufficiently powered for our analyses, accounting conservatively for attrition (~7% at Step One; ~15% at Step Two).

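### Treatment group as a third model level does not fit a design in which every child receives SC-CBT, and no contrast between the two response-defined groups answers Aim 1

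*Combined protocol and SAP*

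**What the plan says.** Section G2 puts repeated measures at level one, and then "the individual children are considered the second level, and the treatment groups are considered the third level". It does not define the treatment groups.

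The design offers few candidates. Section F2 (Treatment) states: "All participants will receive parent-led, stepped-care cognitive-behavioral therapy (SC-CBT". All children start in Step One. At mid-treatment, responders go to maintenance, and a child moves to Step Two under this condition: "If the child does not meet treatment response (i.e., does not improve". G2 uses the word group for that same split. The logistic regression comes "After assessing responder status and determining which participants receive Step Two treatment and which participants move to the maintenance phase", and its purpose is to "determine if there are factors significantly predicting group membership".

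G2 adds a regression discontinuity (RD) analysis on the ground that "this method allows for the use of groups that are similar at baseline, but then are designated by a predetermined selection cut point". The analysis text gives no running variable and no cut-off value. F2 (Assessments) refers the measures to a Section S attachment, which is not part of the documents reviewed.

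Two places hint at a comparator: "Cost-effectiveness analysis examines the relative value of SC-CBT (relative to CBT" in G2, and a mention of two conditions in F2 (Treatment Fidelity/Integrity). F1 and F2 enrol no separate CBT arm.

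G1 justifies 200 children partly by noting that "the suggested power rules range from 20 participants per group, per level". Aim 1 in Section D is the effectiveness of SC-CBT as a whole. The form's question in G2 asks which analysis is primary, and the answer names none.

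**The concern.** A model level is a set of units over which effects vary. Here the only available units are two, and they are created part-way through the trial by the outcome under study. That raises two problems.

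- As a random level, two units carry almost no information on a variance, and more children cannot change that.
- As a fixed effect, group is a post-baseline covariate defined by outcome. Both groups have had Step One and both are SC-CBT, so the difference between them does not compare SC-CBT with anything else.

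At stake is Aim 1. The plan does not say which number answers it, and the between-group contrasts that the text suggests cannot. An analyst could report Step Two against maintenance as the impact of treatment and get an answer driven by how the groups were selected.

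**Working it through.** **The plan's own figure.** The only figure is N = 200. Reading the G1 rule with two groups and three levels gives 20 × 2 × 3 = 120, or 120/(0.93 × 0.85) = 152 after both attrition rates. So 200 clears the rule but is not derived from it. The point does not depend on N: at any N, level three still has two units.

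**Group as a random level.** Units = 2, so df = 2 − 1 = 1. The 95% limits for an SD on 1 df, as multiples of the estimate, are 1/√χ²(0.975) = 0.446 and 1/√χ²(0.025) = 31.9. The matching t multiplier is 12.7.

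Does this damage the change estimate? Not with a random intercept alone, because a within-child difference removes any constant shared by the group. As an illustration under assumed values (170 children, that is 200 × 0.85; reliability 0.8; correlation 0.7; median split on the mid score; built-in mean change −0.80), the fitted baseline-to-post change was −0.824 with SE 0.064 under both two and three levels. Only the intercept's SE moved, from 0.078 to 0.643.

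**Group as a fixed effect.** A group-by-time term would be tested on child-level df, so the 1-df problem does not apply. The problem is selection. Let B, M and P be the baseline, mid and post scores (SD 1, normal, lower is better), with correlations r, and suppose Step Two has no effect. The documents give none of these values, so they are assumptions. If the groups are split on an index S, the group difference in a change Y is

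cov(Y, S)/SD(S) × d, with d = φ(z)/[p(1 − p)], where p is the responder share.

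At 50% response, d = 0.3989/0.25 = 1.596. At 30% or 70%, d = 0.3477/0.21 = 1.656. Contrasts are Step Two minus maintenance, so negative means that Step Two looks better.

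*Response judged on improvement (S = M − B), all r = 0.5, so SD(S) = 1:*
- Baseline to post: covariance r(MP) − r(BM) − r(BP) + 1 = 0.5, giving 0.5 × 1.596 = +0.80, and +0.83 at 30% or 70%. Simulation of 400,000 children per scenario gave 0.80 and 0.82–0.83.
- Mid to post: covariance r(MP) − 1 − r(BP) + r(BM) = −0.5, giving −0.80. The simulated gap went from 0.80 at mid to 0.00 at post, which agrees.

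*Response judged on the mid score (S = M):*
- Baseline to post: covariance r(MP) − r(BM). With equal correlations this is 0. With r(BM) = 0.6 and the other pairs 0.5 it is −0.1, giving −0.16 at 50% and −0.17 at 30% or 70%.
- Mid to post: covariance r(MP) − 1, which is negative whenever r(MP) < 1. At r = 0.5 it gives −0.80.

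So with no Step Two effect, selection makes Step Two look better from mid to post under both rules. (For the improvement rule this needs r(BM) + r(MP) < 1 + r(BP), which holds for the values used.) From baseline to post the sign can be positive, zero or negative.

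**Does any contrast see the SC-CBT effect?** A constant Step One effect shifts both groups equally and cancels. In the simulation (improvement rule, 50% response), the baseline-to-post contrast was 0.80 whether the Step One effect was 0, 0.5 or 1.0 SD. With Step One and Step Two effects of 0.5 SD each, the contrast was 0.29, while the overall benefit was 0.5 + 0.5 × 0.5 = 0.75 SD. The RD is also a Step Two versus maintenance comparison, made at the cut-off, so it does not estimate Aim 1 either.

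**What levels one and two give.** Change in all children is estimable but uncontrolled. A natural improvement of 0.5 SD with no treatment effect gave a mean change of −0.50, the same as a true Step One effect of 0.5 SD.

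**The case against.** The strongest reply is that G2 says only level. It never mentions a random effect, a variance component or a group-level time slope. If group is meant as a fixed effect, the 1-df argument falls away. If it is a random intercept, the change estimate is unharmed. The cohort change that Aim 1 needs is already available from the first two levels. All of that stands, and it limits the point. It does not supply a between-group contrast that answers Aim 1, and it does not name the primary estimate.

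A reader might infer three stronger things that the documents do not support:

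- *That the third level inflates the standard error of the cohort change or shifts its value.* This would need the group level to carry the time effect, and the plan does not specify that.
- *That selection always counts against Step Two from baseline to post.* The text gives no operational response rule and no correlations, and the working shows that the sign can be zero or reversed.
- *That the RD is invalid, or that its score is too coarse.* G2 does state assignment by a predetermined cut point, and the score may be named in Section S. The similar-at-baseline wording is a loose rationale and does not show a failed design. With a stated, fine-grained score the RD can be a legitimate local estimate.

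The groups could also mean therapists or another clustering. If so, the plan has to say so and give their number.

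**Conclusion.** The point holds as a mismatch between the stated model and the design, and it should be corrected before analysis. Two conclusions need no assumed values beyond reading the groups as the split that the design forms. If group is a random level, it has two units and 1 df, with an SD interval of about 0.45 to 32 times the estimate. Whether group is random or fixed, no contrast between Step Two and maintenance, RD included, estimates the effectiveness of SC-CBT.

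The sizes of the selection effects (0.80 SD and the others) are illustrations under assumed correlations, response shares and response rules. They show that the bias can be large and that its baseline-to-post direction is unknown, and they do not predict this trial's result. Regression to the mean from the PARS > 12 entry rule may form part of the cohort change, and the documents do not allow it to be quantified.

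**What to change.** 1. Remove treatment group as a model level. If another grouping is intended, define it and state its number of units. For Aim 1, name as primary the two-level model (occasions within child) of change in all enrolled children, whichever step they received, at a named time point. Report it as uncontrolled change that may include regression to the mean from the entry rule.
2. State that group-by-time contrasts will not be read as a Step Two effect.
3. Keep the RD as a secondary analysis with the estimand Step Two versus maintenance at the cut-off. Use the score that already decides step-up as the running variable, analyse by assigned step, fit a slope on each side and check the functional form. Replace the similar-at-baseline rationale with the assumption that RD needs: in the absence of Step Two, the outcome is continuous in the score at the cut-off. Make the discontinuity claim only if the score is fine-grained, because with a few categories each side's fit must extrapolate to the cut-off.

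This changes analysis wording only. It needs no new data or patients and leaves the step-up rule alone. The cost is a more modest Aim 1 claim and, if the score proves coarse, possible loss of the discontinuity claim.

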## Section D: Purpose and Objectives

The purpose of this study is to implement a parent-led, stepped-care cognitive behavioral therapy to children with ASD and anxiety. Specifically, we will (1) examine the effectiveness of Stepped-Care CBT (SC-CBT; e.g., starting with Step One parent-led, therapist-assisted treatment and then either maintenance or Step Two therapist-directed CBT), (2) examine the potential predictors of response to Step One that could be used as baseline tailoring variables to match children to the best level of care (i.e., Step One or CBT), and (3) examine the economic value of using a cost-effectiveness approach of SC-CBT. We expect that through Stepped-Care CBT, children’s anxiety levels will lessen.

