**Section F: Design/Procedure****F1. Design**

Select one category that most adequately describes your research:

d) Questionnaire/survey/interview

Discuss the research design including but not limited to such issues as: probability of group assignment, potential for subject to be randomized to placebo group, use of control subjects, etc.

A total of 200 children (aged 4-14) with a diagnosis of ASD and co-occurring anxiety and their parent/legal guardian will participate and receive SC-CBT treatment. In addition, all participants will be asked to cooperate in assessments that will occur at baseline, mid-treatment, post-treatment, and 3-month follow-up.

Inclusion Criteria:

- 1) The child is between the ages of 4 to 14 upon enrollment with a) an established diagnosis of ASD made by a standardized assessment (e.g., Autism Diagnostic Observation Schedule-Second Edition; Childhood Autism Rating Scale-Second Edition); and/or b) a score of 65 and above on the Social Responsiveness Scale-Second Edition (SRS-2).
- 2) The child has clinically elevated symptoms of anxiety and/or OCD as indicated by a Clinical Severity Rating of  $\geq 4$  from the Anxiety Disorders Interview Schedule (ADIS), made on diagnoses endorsed on the Mini-International Neuropsychiatric Interview for Children and Adolescents (MINI-Kid) at baseline assessment, and the Pediatric Anxiety Rating Scale  $> 12$ .
- 3) Anxiety and/or OCD is the primary presenting problem and the independent evaluator (IE) determines that the child is appropriate for the intervention focus.
- 4) One parent/guardian is able and willing to participate (i.e., parent-led therapist assisted treatment, attend study assessments).
- 5) The child has a Full Scale and Verbal Comprehension IQ  $> 70$  as assessed on the Differential Ability Scales-Second Edition (DAS-II) or Wechsler Abbreviated Scale of Intelligence-Second Edition (WASI-II). This level of intellectual ability is frequently used to demarcate the boundary of "high functioning"  $\pm$  ASD, and we and others have adopted this in our CBT trials for children with ASD to achieve acceptable external validity.
- 6) Both parent and child are able to read and/or understand English

Exclusion Criteria:

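### The regression discontinuity in G2 can estimate only Step Two versus maintenance at the response cut, and baseline similarity is not what makes it valid

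*Combined protocol and SAP*

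**What the plan says.** Section D gives the first aim as to "examine the effectiveness of Stepped-Care CBT", meaning the whole sequence: "starting with Step One parent-led, therapist-assisted treatment and then either maintenance or Step Two therapist-directed CBT".

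F2 (Treatment, Step One, Step Two) gives SC-CBT to every participant and starts all of them on Step One. A mid-treatment assessment follows. Responders go to maintenance and the others to Step Two. Entry criterion 2 in F1 begins "The child has clinically elevated symptoms of anxiety and/or OCD" and also requires a Pediatric Anxiety Rating Scale score above 12.

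G2 plans a multilevel model in which "the treatment groups are considered the third level". Within it sits the RD: "This will allow us to examine the impact of treatment, without the use of random assignment", because "this method allows for the use of groups that are similar at baseline, but then are designated by a predetermined selection cut point". The next paragraph adds that "binary logistic regression will be utilized in an attempt to determine if there are factors significantly predicting group membership", with anxiety severity among the candidate factors.

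G1 states that 200 participants give enough power for the primary and secondary aims. It cites a rule of 20 per group per level and attrition of about 7% at Step One and 15% at Step Two. It gives no effect size.

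**The concern.** G2 does not say which treatment effect the RD estimates. A cut-based comparison informs only on what differs between the two sides of the cut. Here that is Step Two against maintenance, which is one component of SC-CBT. If the result were reported simply as the effect of treatment, it could be taken as evidence for the whole programme, which it is not.

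The stated basis is also off. An RD does not need the two groups to be alike at baseline. It needs assignment by a cut on a measured score, no manipulation of that score, an expected outcome under each condition that is continuous at the cut, and a correctly modelled score. A reader who takes the groups as similar might compare them directly and call the difference a Step Two effect.

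**Working it through.** **Step 1. The plan's own figure.** With 2 groups and 3 levels, the G1 rule gives 20 × 2 × 3 = 120. Dividing by 0.93 gives 130, and by 0.93 × 0.85 gives 152. Two other readings come close to 200: 20 × 2 × 4 = 160, or 203 after both attrition rates; and 20 × 3 × 3 = 180, or 194 after 7%. The documents support neither. The figure of 200 can be neither confirmed nor called wrong, and the rule says nothing about an RD.

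**Step 2. Which contrast is available.** This needs no assumed number. Children who fail the F1 entry cuts are not enrolled, so those cuts give no comparison. All enrolled children have Step One. The only remaining cut is response at mid-treatment, so the RD jump is Step Two minus maintenance for children at that cut.

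**Assumptions from here on (none is in the documents).** Normal scores with SD 1 and higher meaning more anxiety; equal correlation r between visits, 0.5 to 0.8; non-responder share p, 0.3 to 0.7.

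**Step 3. RD versus SC-CBT effect.** SC-CBT effect = Step One effect + p × Step Two effect. Simulated RD (172 children, r = 0.65, response judged on change, 2,500 runs per setting):

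| Step One | Step Two | p | RD | SC-CBT effect |
|---|---|---|---|---|
| 0.5 | 0 | 0.5 | 0.00 | 0.50 |
| 0 | 0.5 | 0.3 | 0.50 | 0.15 |
| 0 | 0.5 | 0.5 | 0.50 | 0.25 |
| 0 | 0.5 | 0.7 | 0.50 | 0.35 |

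**Step 4. Baseline gap, Step Two minus maintenance.** Let k = φ(z_p) / (p(1 − p)), which is 1.596 at p = 0.5 and 1.656 at p = 0.3 or 0.7.
- Response judged on mid-treatment level: gap = r × k, from 0.5 × 1.596 = 0.80 to 0.8 × 1.656 = 1.32 SD.
- Response judged on change from baseline: gap = −√((1 − r)/2) × k, from −0.316 × 1.596 = −0.50 to −0.5 × 1.656 = −0.83 SD.
- Response judged on a 30–50% reduction (baseline mean 4–6 SD above zero): −0.38 to +0.74 SD by simulation, and within 0.2 SD of zero in one third of settings.

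Similarity can occur, but only by coincidence of the rule.

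**Step 5. What dissimilar groups do to each analysis, with no true Step Two effect.**
- RD with separate slopes and the baseline score (172 children): mean estimate within 0.007 SD of zero, rejection rate 4.4–6.0%, under both the level and the change rule.
- Unadjusted baseline-to-post change, change rule: groups differ by √((1 − r)/2) × k = 0.50 to 0.83 SD, making Step Two look harmful.
- The same contrast under the level rule: no bias, because cov(post − baseline, mid) = r − r = 0. The raw post scores still differ by r × k = 0.80 to 1.32 SD, and mid-to-post change by (1 − r) × k = 0.32 to 0.83 SD.

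**Step 6. Aim 1.** If only the top fraction q of baseline scores enters (cut-off c), regression to the mean = (1 − r) × φ(c)/q. With q = 0.7 and r = 0.8 this is 0.2 × 0.497 = 0.10 SD. With q = 0.3 and r = 0.5 it is 0.5 × 1.159 = 0.58 SD. That is apparent improvement with no treatment effect.

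**Step 7. Detectable effect for the RD (80% power, two-sided 5%).** MDE = 2.80 × √(DE × V / (N p(1 − p))). V = 1 − 2r²/(1 + r) is the residual variance, and the design effect DE is about 2.7 with separate linear slopes. N runs from 200 × 0.93 × 0.85 = 158 to 200 × 0.93 = 186.
- Lowest: 2.80 × √(2.75 × 0.289 / (186 × 0.25)) = 0.37 SD.
- Highest: 2.80 × √(2.70 × 0.667 / (158 × 0.21)) = 0.65 SD.
- Adding quadratic terms raises DE to about 5 and the range to 0.50–0.88 SD.
- If the top 30–70% of baseline scores enter, the enrolled baseline SD is 0.514 to 0.702. In those units the linear range is 0.37/0.702 = 0.52 to 0.65/0.514 = 1.27.
- At 20 per group (N = 40, p = 0.5): 0.79 to 1.20 SD with linear slopes.

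**The case against.** A fair reply has several parts.

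- G2 does not tie the RD to Aim 1. The single arm is disclosed, and Section D's expectation that anxiety will fall is within-cohort change, which the multilevel model can estimate. This stands: the Aim 1 remedy is mainly a label.
- The contrast can be inferred, since G2's next paragraph names Step Two and maintenance as the groups. True, but the RD text itself speaks only of treatment, in answer to a form question on how the analyses serve the study's purposes.
- Baseline similarity may mean similarity near the cut, which is a real RD check. G2 does not say so.
- F2 describes non-response as lack of improvement, which points to change rather than level. The largest gap in Step 4 (up to 1.32 SD) is therefore the less likely case.

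Stronger readings are tempting, but the documents do not support them:
- *The RD is biased because the groups differ.* It is not, if correctly specified (Step 5).
- *The groups must differ at baseline.* That depends on the response rule. The logistic regression serves Aim 2 and only looks for predictors; it does not show a difference.
- *The plan will use an unadjusted group contrast.* G2 makes groups the third level but proposes no such contrast.
- *The response score is missing.* It may be in the Section S attachments, which were not supplied, so its absence is not counted here.
- *200 children are too few.* Nothing in the documents allows that conclusion.

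**Conclusion.** G2 is wrong as written on two counts and should be corrected; the flaw does not invalidate the trial. First, the RD can estimate only Step Two versus maintenance at the response cut and cannot speak for SC-CBT overall. This follows from Sections D, F2 and G2 alone. Second, baseline similarity of the whole groups is not the condition for a valid RD. For Aim 1 the plan has only uncontrolled change over time in children enrolled for elevated anxiety.

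Every magnitude above is illustrative. Correlations, response share, selection fraction and response rule are all assumed. The direction is firm: the RD and the SC-CBT effect can differ widely either way (0 against 0.50 SD; 0.50 against 0.15 SD), and regression to the mean alone could supply 0.10–0.58 SD of apparent improvement.

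**What to change.** 1. In G2, state that the RD estimates Step Two versus maintenance at the response cut only and is not evidence for SC-CBT overall.
2. Replace the sentence on baseline similarity with the RD conditions: assignment follows the cut on a measured score; the score is not manipulated; the expected (potential) outcome under each condition is continuous at the cut; the functional form of the score is modelled and checked. Keep the RD in the planned mixed model, with post and follow-up scores as outcomes, so that children with missing visits are retained. Include a Step Two indicator, the existing response score centred at its cut, their interaction and the baseline score. If no continuous score lies behind response, say that the RD cannot be run. Do not read an unadjusted group contrast as a Step Two effect.
3. Report Aim 1 as within-cohort change from the mixed model, labelled as uncontrolled and subject to time effects and regression to the mean.
4. Do not extend G1's power statement to the RD on the 20-per-group rule. Do not write 0.37–0.65 SD into the plan either: it assumes an unselected population and a linear model, and is larger otherwise.

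The cost is wording and one model specification, with no new data, visits or children. The downside is a more modest claim for the RD and for Aim 1.
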